	Screening and Baseline Assessments ⁷	Registration ⁷	Day of Intervention ⁸	1 day follow-up (+ 3 day window)	1 month follow-up (± 7 day window)	3 month follow-up (± 7 day window)	6 month follow-up (± 7 day window)
Informed consent	X						
Demographic information and medical history ¹	X						
Physical exam, height, and weight ²	X						
AE assessment ³	X		X	X	X		
HF severity assessments ⁵	X (collect HF data for ≥ 1 week prior to the day of intervention)				X	X	X
HFRDIS ⁶	X			Weekly during follow-up per Section 5.2			
PROMIS SF4a ⁶	X				X	X	X
PGIC score ⁶					X	X	X
Registration ⁷		X					
SGB Intervention ⁸			X				
Horner's sign assessment post-SGC intervention ⁸			X				
Timed vitals during recovery ⁹			X				
Follow-up contact ¹⁰				X	X	X	X
Weekly reminders ¹¹				X			
Hot flash diary ^{12, 5}				X			

STU#:00208657

Version 3.1

11/25/2019

1. Demographic information and medical history to include: age, body mass index, race, years of education, marital status, Gleason score, duration of hot flashes (months), type of ADT (specify) per Section 5.4. Height and weight to be collected for BMI calculation. Pathology report to be collected to determine Gleason Score.
2. Brief physician-directed physical exam to focus on cervical range of motion and anterior cervical anatomy per Section 5.2.
3. Refer to Section 5.6 for details on the collection of AEs and SAEs. In brief, AEs that are related to the intervention (irrespective of expectedness) will be collected from the time of consent (baseline) through the 30 days after the intervention (the 1 month follow-up visit). All SAEs (irrespective of attribution/relatedness or expectedness) will be collected from the time of consent (baseline) through 30 days after the intervention (the 1 month follow-up visit).
4. Screening labs not required for this study; not a standard of care
5. Patient-reported hot flash (HF) frequency and HF intensity to be collected, based on the participant's hot flash diary. These values will be used to calculate a HF severity score, per Section 3.0. Participants must complete the diary for at least 1 week prior to receipt of the intervention to be able to determine the baseline HF severity score.
6. HFRDIS, PROMIS SF4a, and PGIC score questionnaires to be administered via REDCap. Other methods may also be used (i.e. in person, over the phone, through mail or email, etc.) if required.

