7. All screening assessments to be conducted 0-14 days prior to registration, unless otherwise indicated. Participants must register to the trial prior to receipt of the study intervention. Refer to Section 12.0 for registration instructions.
8. The SGB intervention should take place AFTER registration and within 1-2 weeks after the baseline/screening assessments per Section 5.2. Participants are to complete the diary daily starting at least 1 week prior to receipt of the SGB intervention. Details of the SGB intervention and Horner's sign assessment are described in Section 5.2
9. Vitals are to be assessed approximately every 5 minutes for approximately 20-30 minutes while participants are in recovery, after receipt of SGB.
10. Participants will be contacted for follow-up via their preferred method of contact (phone call, in-person visit, email, etc.) 1 day and 1 month after the intervention to collect AE/SAE data. They will also be contacted (via REDcap or other means) at 1 month, 3 months, and 6 months to collect information for secondary outcomes.
11. Qualified research staff may contact participants via their preferred method of contact (phone call, in-person visit, email, REDcap generated email, etc.) approximately once a week (or less frequently as needed) throughout the course of the study to remind participants to comply with study procedures, including but not limited to: scheduling appointments; completing the HF diary; completing the HFRDIS, PROMIS SF4a, and PGIC score questionnaires; assessing AEs/SAEs.
12. Participants will be instructed to begin completing the hot flash diary at the time of screening/baseline assessments. Participants are to complete the diary daily starting at least 1 week prior to receipt of the SGB intervention and through the 6-month follow-up time point. Weekly phone calls (or other preferred method of contact) may be used to remind participants to comply.

STU#:00208657

Version 3.1

11/25/2019

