SGB is considered safe when performed with image guidance and by an experienced injectionist. The published rate of adverse events with SGB, pre-dating image guided procedures, is 0.17%. Severe injury related to SGB is very rare. The incidence of unanticipated bleeding complications following SGB is 1:100,000. It follows that image guided injections, as with fluoroscopy, would have far fewer complications, as critical vascular or neural structures can be visualized in real time and thus can be avoided. [name] has been performing this injection for 20 years and has 3 other active clinical trials assessing the effects of SGB in women, including a study funded by the National Institute on Aging, of which [name] is the PI.

In none of these studies has an adverse event occurred. Adverse events will be assessed at the time of the study intervention, at discharge from the post-anesthesia care unit (PACU), at the 24 hour post-injection follow-up, and at the 1 month follow-up. All adverse events that are possibly, probably, or definitely related to the intervention will be collected. All SAEs, regardless of attribution, will be collected. Refer to Section 5.6 for details.

The following potential adverse events are expected:

Risks of Stellate Ganglion Injection

Stellate ganglion injection carries the potential risk of infection, bleeding, transient seizure, or nerve injury which may result in paresthesia or weakness. Risks are mitigated and effectively minimized with the use of fluoroscopic guidance and confirmatory contrast dye study during the SGB.

Risks Related to Needle Placement

Temporary bruising or swelling at the site of the injection on the right anterior neck

Hematoma (pocket of blood caused by bleeding from a broken blood vessel)

Injury to the nerves around the injection site

Puncture of the lung or a blood vessel which may compress the lung and require further medical treatment.

Infection of the tissues of the neck, nerves, bone or disc material in the area of injection

Risks Related to spread of local anesthetic

Allergic reaction to local anesthetics (lidocaine or bupivacaine) or contrast dye

Temporary voice hoarseness

Temporary difficulty swallowing

Temporary weakness of the right diaphragm which may cause shortness of breath or mild difficulty in breathing

Temporary high or low blood pressure

Temporary numbness on the anterior neck region and right shoulder

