5.6.2 Definitions & Descriptions

5.6.2.1 Adverse Events

An adverse event (AE) is any untoward medical occurrence in a patient receiving study treatment and which does not necessarily have a causal relationship with this treatment. An AE can therefore be any unfavorable and unintended sign (including an abnormal laboratory finding), symptom, or disease temporally associated with the use of an experimental intervention, whether or not related to the intervention.

Recording of AEs should be done in a concise manner using standard, acceptable medical terms. In general, AEs are not procedures or measurements, but should reflect the reason for the procedure or the diagnosis based on the abnormal measurement. Preexisting conditions that worsen in severity or

STU#:00208657

Version 3.1

11/25/2019

frequency during the study should also be recorded (a preexisting condition that does not worsen is not an AE). Further, a procedure or surgery is not an AE; rather, the event leading to the procedure or surgery is considered an AE.

If a specific medical diagnosis has been made, that diagnosis or syndrome should be recorded as the AE whenever possible. However, a complete description of the signs, symptoms and investigations which led to the diagnosis should be provided. For example, if clinically significant elevations of liver function tests are known to be secondary to hepatitis, "hepatitis" and not "elevated liver function tests" should be recorded. If the cause is not known, the abnormal test or finding should be recorded as an AE, using appropriate medical terminology (e/g/ thrombocytopenia, peripheral edema, QT prolongation).

For this study, only AEs that are possibly, probably, or definitely related to the intervention will be collected (Refer to Section 5.6.2.3 for separate criteria for collection of SAEs). Expected symptoms are listed in Sections 5.2 and 5.5 and/or can be found in the U.S. FDA drug package insert. AEs that are possibly, probably, or definitely related to the intervention will be collected from the time of signing informed consent until 30 days after receipt of the intervention at the 1 month follow-up time point. Refer to Sections 5.2 and 5.3 for additional information on the time points for AE collection.

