5.6.2.3 Serious Adverse Events

All serious adverse events (SAEs), regardless of expectedness and attribution, occurring from the time of signed informed consent, through 30 days after the last administration of study drug (i.e. at the 1 month follow-up time point), must be reported upon discovery or occurrence.

An SAE is defined in regulatory terminology as any untoward medical occurrence that:

- **Results in death.**
- **Is life-threatening.**
The patient was at risk of death at the time of the event; it does not refer to an event that hypothetically might have caused death if it were more severe.
- **Requires *in-patient hospitalization or prolongation of existing hospitalization for ≥ 24 hours.***
- Results in *persistent or significant disability or incapacity.*
- Is a *congenital anomaly/birth defect.*
- Is an *important medical event.*

Any event that does not meet the above criteria, but that in the judgment of the investigator jeopardizes the patient, may be considered for reporting as a serious adverse event. The event may require medical or surgical intervention to prevent one of the outcomes listed in the definition of "Serious Adverse Event". For example: allergic bronchospasm requiring intensive treatment in an emergency room or at home; convulsions that may not result in hospitalization; development of drug abuse or drug dependency.

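### AE/SAE collection runs to day 30, but the last required safety contact may be made on day 23, leaving up to 7 days without a required enquiry

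*Combined protocol and SAP*

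**What the plan says.** The collection period is stated three times, each time as 30 days and each time tied to the 1-month follow-up:

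- Schedule of Events, footnote 3: related AEs "will be collected from the time of consent (baseline) through the 30 days after the intervention (the 1 month follow-up visit". The footnote gives the same end point for all SAEs.
- Section 5.6.2.1, for related AEs: "until 30 days after receipt of the intervention at the 1 month follow-up time point".
- Section 5.6.2.3, for all SAEs: "through 30 days after the last administration of study drug (i.e. at the 1 month follow-up time point), must be reported upon discovery or occurrence".

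The column heading in the Schedule of Events gives that visit a tolerance in both directions: "1 month follow-up (± 7 day window".

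Three places show that this is also the last required safety enquiry. The AE row of the schedule has no mark at 3 or 6 months. Footnote 10 says that participants are contacted "1 day and 1 month after the intervention to collect AE/SAE data", and gives the 3- and 6-month contacts a different purpose (secondary outcomes). Section 5.5 ends its list of AE assessments "at the 24 hour post-injection follow-up, and at the 1 month follow-up".

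Footnote 11 lets staff make roughly weekly reminder contacts and names AE/SAE assessment among their possible subjects. They are permitted rather than required, and may be less frequent than weekly. Section 5.2 describes weekly contact as something done if needed, to keep men completing the follow-up measures.

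**The concern.** A fixed 30-day period and a visit that may fall a week either side of its target are not the same moment, yet the plan uses each to define the other. If the visit is early, the collection period is still open after the last contact at which anyone must ask about adverse events. If it is late, the enquiry runs past the period.

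Adverse events related to the block are secondary outcome 7 in Section 3.0. They are to be summarised by severity, type and attribution (Section 17.0, Statistical Plan), in a pilot meant to lead to a larger randomised sham-controlled trial. The study is small: one event is 1/18 = 5.6% of men if 18 are enrolled and 1/14 = 7.1% if 14 are. What is at stake is whether every man is asked about the same 30 days.

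**Working it through.** **Inputs**

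- Stated length of collection after the intervention: 30 days (footnote 3; Sections 5.6.2.1 and 5.6.2.3).
- Visit tolerance: ±7 days (Schedule of Events, column heading).
- Length of 1 month: taken as 30 days, because all three statements of the period equate the two.
- Required AE/SAE contacts after discharge: 1 day and 1 month (footnote 10; Section 5.5 agrees).

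**Permitted timing of the closing contact**

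- Earliest: 30 − 7 = day 23.
- Latest: 30 + 7 = day 37.

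**Days left after an earliest-permitted contact**

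- 30 − 23 = 7 days, namely days 24 to 30.
- Share of the stated period: 7/30 = 23.3%.

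**If 1 month is a 31-day calendar month.** Earliest contact is 31 − 7 = day 24, leaving 30 − 24 = 6 days, or 6/30 = 20%. The result hardly changes.

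**When the gap arises**

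| Day of the 1-month contact | Days of the 30 not covered by required enquiry |
|---|---|
| 23 | 7 |
| 25 | 5 |
| 28 | 2 |
| 30 to 37 | 0 |

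The gap exists only for men seen before day 30. For men seen after day 30 the issue is reversed: an event starting between day 31 and the contact can be mentioned although it lies outside the stated period. The protocol text does not say that onset dates are recorded so that such events can be separated.

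**Other data streams.** The daily diary and weekly HFRDIS continue for 6 months, but Section 5.4 shows that they record hot flashes and interference, not adverse events.

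**Scale of related events.** Section 5.5 cites an adverse event rate of 0.17%, from before image guidance. With at most 18 men, 18 × 0.0017 = 0.03 related events are expected in total, before restricting to the last week. This figure does not cover SAEs from other causes, which the plan also collects.

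**After the fix.** If the closing contact cannot fall before day 30, the uncovered time is 30 − 30 = 0 days for every man contacted.

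**The case against.** The strongest reply is that the duty to collect is written in days, while the ±7 days is a column heading that also covers the questionnaires. On that reading the specific 30-day duty governs, and a site that stopped at day 23 would not have met it. SAEs must be reported upon discovery or occurrence, which does not depend on a visit. Section 5.2 gives men the chance to raise new concerns at the 1-, 3- and 6-month interactions and tells them to contact the investigator about urgent ones. Footnote 11 allows AE questions during reminder contacts. The local-anaesthetic effects are said in Section 5.5 to resolve within hours, so a late related event is unlikely.

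Much of this stands, and it limits the size of the point. It does not remove it. The three statements of the 30-day duty each name the 1-month contact as its end, so the text does not tell a site that a further enquiry is needed after an early visit. The other routes are optional or depend on someone volunteering the event. Section 5.5 also lists infection of neck tissue, nerve, bone or disc, which is not tied to the recovery period, and the SAE rule covers every cause. If the visit itself is meant to end collection, the period runs from 23 to 37 days across men and the stated 30 days is wrong, so the passages need reconciling on either reading.

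Four stronger inferences are tempting, and the documents do not support them:

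- **That days 24 to 30 go unobserved.** They lack a required enquiry; optional contacts and spontaneous reports may still pick events up.
- **That the adverse event results would be understated.** That needs an early contact, an onset in the remaining days and no report by another route. No 30-day rate is planned either; the outcome is number and type of events.
- **That the gap could reach 9 days, by reading 1 month as 28 days.** The protocol ties 1 month to 30 days.
- **That a persisting injury would have no recorded outcome.** Section 5.6.2.5 asks for the outcome of an SAE if known, and the institutional monitoring plan cited in Section 5.6 is not available here, so this cannot be established.

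**Conclusion.** The 30-day definition and the visit window are inconsistent. As written, the last required AE/SAE contact may fall on day 23, leaving up to 7 of the 30 days (23%) without a required enquiry, so an event with onset on days 24 to 30 could be missed. The period covered by required enquiry can also differ between men. The result rests on 1 month meaning 30 days, as the protocol itself states, and on a visit at the early edge of its window; for visits on or after day 30 there is no gap. The expected number of affected events is small. The change is still worth making, because related events are a stated outcome, the protocol itself chose 30 days, and the repair is cheap.

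**What to change.** In the Schedule of Events and in footnotes 3 and 10, give the closing AE/SAE contact its own one-sided window: not before day 30, for example day 30 +7. Keep ±7 days for the 1-month questionnaires. The schedule already does this for the 1-day contact, which is allowed +3 days and no earlier. Sections 5.5, 5.6.2.1 and 5.6.2.3 should then refer to that closing contact rather than to the 1-month visit. Record the onset date of each event and apply the 30-day limit by onset date, so that a contact on day 37 does not extend the period.

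The cost is a minor amendment to the schedule, the footnotes and the matching text. Men whose 1-month questionnaires are completed before day 30 will need a brief second contact. Phone or email is enough, since footnote 10 already allows the participant's preferred method.

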5.4 Outcome Measures

Hot Flash Diary

Daily Hot Flash Diaries (daily throughout entire study): daily diaries include measures of: (a) hot flashes frequency while awake; (b) the number of night sweats; (c) intensity of hot flashes while awake, with

0 = none

1 = mild (1 or 2 episodes of heat)

2 = moderate (3 to 4 episodes of heat with discrete sweating)

3 = severe (5 or more sudden episodes of heat accompanied by sweating, sleep disturbance, feelings of irritation or anxiety).

Hot Flash Related Daily Interference Scale (HFRDIS)(34)

This validated measure assesses the impact of hot flashes on overall quality of life as well as on work, social activities, leisure activities, sleep, mood, concentration, relations with others, sexuality, and enjoyment of life. A total of 10 areas are assessed with a 0-10 scale. The maximum score, demonstrating the most severe interference of HF is 100.

PROMIS SF4a (sleep)

One of the PROMIS measures, this is a 4-item questionnaire that queries sleep duration, quality, and interruption.

Patient Global Impression of Change

This outcome has the participant assess how much improvement they believe they have experienced from an intervention. This will be collected at 1, 3, and 6 month time points.

General Demographic and Health Status Information

We will obtain sociodemographic and clinical variables based on participant report, including

- age
- body mass index
- race
- years of education
- marital status
- Gleason score
- duration of hot flashes (months)
- type of ADT (specify)

5.5 SGB Risks & Safety:

Stellate ganglion injections are commonly performed in the U.S., have been in clinical use for more than 50 years, and are considered safe and effective in treating a variety of neuropathic syndromes and ischemic pain states and cardiac dysrhythmias (Complex Regional Pain Syndrome Type I and II, herpes zoster, frostbite, Raynaud's syndrome, vascular headaches, refractory ventricular tachycardia, pulmonary artery hypertension, for example). Several more recent studies have demonstrated clinical effectiveness in treating vasomotor symptoms

STU#:00208657

Version 3.1

11/25/2019

in women and no adverse events have been reported from these more recent trials.

SGB is considered safe when performed with image guidance and by an experienced injectionist. The published rate of adverse events with SGB, pre-dating image guided procedures, is 0.17%. Severe injury related to SGB is very rare. The incidence of unanticipated bleeding complications following SGB is 1:100,000. It follows that image guided injections, as with fluoroscopy, would have far fewer complications, as critical vascular or neural structures can be visualized in real time and thus can be avoided. [name] has been performing this injection for 20 years and has 3 other active clinical trials assessing the effects of SGB in women, including a study funded by the National Institute on Aging, of which [name] is the PI.

In none of these studies has an adverse event occurred. Adverse events will be assessed at the time of the study intervention, at discharge from the post-anesthesia care unit (PACU), at the 24 hour post-injection follow-up, and at the 1 month follow-up. All adverse events that are possibly, probably, or definitely related to the intervention will be collected. All SAEs, regardless of attribution, will be collected. Refer to Section 5.6 for details.

The following potential adverse events are expected:

Risks of Stellate Ganglion Injection

Stellate ganglion injection carries the potential risk of infection, bleeding, transient seizure, or nerve injury which may result in paresthesia or weakness. Risks are mitigated and effectively minimized with the use of fluoroscopic guidance and confirmatory contrast dye study during the SGB.

Risks Related to Needle Placement

Temporary bruising or swelling at the site of the injection on the right anterior neck

Hematoma (pocket of blood caused by bleeding from a broken blood vessel)

Injury to the nerves around the injection site

Puncture of the lung or a blood vessel which may compress the lung and require further medical treatment.

Infection of the tissues of the neck, nerves, bone or disc material in the area of injection

Risks Related to spread of local anesthetic

Allergic reaction to local anesthetics (lidocaine or bupivacaine) or contrast dye

Temporary voice hoarseness

Temporary difficulty swallowing

Temporary weakness of the right diaphragm which may cause shortness of breath or mild difficulty in breathing

Temporary high or low blood pressure

Temporary numbness on the anterior neck region and right shoulder

Temporary numbness or weakness of the arms and legs with short term inability to talk or swallow

STU#:00208657

Version 3.1

11/25/2019

*As the half-life of bupivacaine is 6-8 hours, all of the above would resolve within this 6-8 hour time period

*Antidotes to local anesthetic toxicity, including propofol and lipid emulsion, are immediately available in the Omnicell of the Pain Clinic

*A crash cart is immediately available in the recovery room of the Pain Clinic

*The Pain Clinic is staffed by 3 anesthesiologists daily, in addition to 2-3 RNs

Risks Related to Fluoroscopy

The dose of radiation used in the procedure is approximately equal to 25 days of natural environmental radiation the average person receives in the United States.

Radiation Dosimetry Form

